#### **3.1.3.** Analysis of efficacy parameters

Main efficacy parameters of the studied MD:

1. Change in the overall score on the WOMAC scale (WOMAC-T) on Visit 3 (week 13), Visit 5 (week 25) compared to the basal value on Visit 0 (screening) of the open study and compared to the basal value on Visit 1 (week 1) of the IA/PAAG-SI/OA/2019 study;

2. Change in the pain subscale score (WOMAC-A) on Visit 3 (week 13), Visit 5 (week 25) compared to the basal value on Visit 0 (screening) of the open study and compared to the basal value on Visit 1 (week 1) of the IA/PAAG-SI/OA/2019 study;

3. Change in the score for stiffness subscale (WOMAC-B) and functional performance (WOMAC-C) at Visit 3 (week 13), Visit 5 (week 25) compared to the basal value at Visit 0 (screening) of open study and compared to the basal value at Visit 1 (week 1) of the study IA/PAAG-SI/OA/2019;

4. The change in the severity of pain in the target knee on a 100-mm VAS at Visit 2 (week 1), Visit 3 (week 13), Visit 5 (week 25) compared to the basal value at Visit 0 (screening) of open safety study and compared to the basal value at Visit 1 (week 1) study IA/PAAG-SI/OA/2019;

5. Evaluation of the effectiveness of treatment by the patient, parameter OEP (on a scale from 1-clear deterioration to 6-significant improvement) on Visits 3 and 5 (parameters OEP-w13 and OEP-w25, respectively);

6. Evaluation of the effectiveness of treatment by the investigator, parameter OEI (on a scale from 1-clear deterioration to 6-significant improvement) on Visits 3 and 5 (parameters OEI-w13, OEI-w25, respectively);

7. Assessment of the total number of paracetamol tablets taken (one tablet = 500 mg) starting from day 1 on Visits 3 and 5 (PARACETAMOL -w13 and PARACETAMOL-w25, respectively);

8. Assessment of the total number of NSAID tablets taken starting from day 1 on Visits 3 and 5 (NSAID-w13 and NSAID-w25, respectively);

9. The parameter JSN of the target knee joint at Visit 5 of the open study compared to the basal value on Visit 0 of the IA/PAAG-SI/OA/2019 study retrospectively.

All performance parameters will be analyzed both among all patients included in open study no. IA/PAAG-SI/OA/2020 (using descriptive statistics) and in subgroups of patients:

- those who received only one course of injections in the placebo-controlled study IA/PAAG-SI/OA/2019;
- those who received two courses of therapy both in the placebo-controlled and at Visit 1 (and as per the indications at Visit 2) of the open study;
- those who received two courses of therapy both in the placebo-controlled and at Visit 3
  (and as per the indications at Visit 4) of the open study.

For comparison between these subgroups, variance analysis will be used (for quantitative parameters other than those based on WOMAC), covariance analysis (for quantitative parameters based on WOMAC, in this case the initial value of WOMAC in the double-blind phase of the study will be used as a covariate, and the results will be presented as the average, calculated by the least squares method), or the "Chi-square" criterion (for qualitative parameters), followed by the application of multiple comparison criteria (if necessary).

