Patients who signed the informed consent form to participate in an open study IA/PAAG-SI/OA/2020 to evaluate the safety and effectiveness of MD NOLTREXTM, in the case when pain in the target knee joint in the study IA/PAAG-SI/OA/2019 remained the same or increased (on a 100-mm visual analogue scale [VAS]) compared to the rating at Visit 1 of the study IA/PAAG-SI/OA/2019 (or if a decrease in pain severity is less than 40— compared to the rating at Visit 1 of the study IA/PAAG-SI/OA/2019), will receive the injection of MD NOLTREXTM in the target knee (Group A). MD will be administered in accordance with the instructions for use of MD NOLTREXTM: 4.0 ml per injection (2.5 + 1.5 ml, or 2.0 + 2.0 ml from two syringes through one needle [one puncture]) at intervals of one week. The course in an open study is a maximum of 2 injections (the first - at Visit 1, the second - at Visit 2). The number of injections is determined by the doctor depending on the stage of gonarthrosis and the clinical response. In order to avoid overfilling the joint with dense slowly resorbable material, at the good clinical result (reducing the pain severity on a 100 mm VAS by Visit

2 by more than 40— compared to the basal level in the open study[1]), the course of injections will be discontinued.

Patients included in the open part of the study, who have the severity of pain in the target knee joint at the time of inclusion in the open part of the study decreased by 40— or more compared to the assessment on Visit 1 of the IA/PAAG-SI/OA/2019 study, or those who cannot be re-injected with MD NOLTREXTM, a re-injection of MD NOLTREXTM will not be performed on Visits 1 and 2 of the open study (Group B).

A repeated course of MD NOLTREXTM injections in an open study is not possible if any of the following criteria are met:

- 1. Documented intolerance of the studied MD NOLTREXTM;
- 2. Active inflammation in the target knee joint (edema, hyperemia, effusion) at the time of inclusion in the study;
- 3. Inflammatory diseases of the skin and soft tissues in the area of the intended introduction of the studied MD into the target joint;
- 4. History of venous thrombosis and thromboembolism;
- 5. Deviations from the norm in the coagulogram (activated partial thromboplastin time [APTT], prothrombin time [PT], prothrombin index, fibrinogen);
- 6. Hemophilia and other hemorrhagic diatheses, as well as taking anticoagulants and disaggregants;

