At Visit 3 additional evaluation will be conducted to assess the feasibility and possibility of reinjections with MD NOLTREXTM among patients of group B. If at Visit 3 of the open study pain remains the same in the target joint of the study IA/PAAG-SI/OA/2019 or increases in intensity (as per 100-mm VAS) in comparison with the assessment at Visit 1 of the study IA/PAAG-SI/OA/2019 (or if a decrease in pain severity is less than 40% when compared to the rating at Visit 1 of the study IA/PAAG-SI/OA/2019), in the absence of the above criteria for non-treatment with the studied MD, at Visit 3 of open study the injection of MD NOLTREXTM into the target knee joint will be performed. MD will be administered in accordance with the instructions for medical use of MD NOLTREXTM: 4.0 ml per injection (2.5 + 1.5 ml, or 2.0 + 2.0 ml from two syringes through one needle [one puncture]) once or twice at intervals of one week. The treatment course in the framework of an open study among patients of Group B is a maximum of 2 injections (the first - at Visit 3, the second - at Visit 4). The number of injections is determined by the doctor depending on the stage of gonarthrosis and the clinical response. In order to avoid overfilling the joint with dense slowly resorbable material, at the good clinical result (reducing the pain severity on a 100 mm VAS by Visit 2 by more than 40— compared to the basal level in the open study[1]), the course of injections will be discontinued. The open nature of the study in one group is determined by the main purpose of the study - to assess the safety of MD NOLTREX[™] with a single or repeated course of use. Placebo safety data at the 6-month point (visit 5) in the IA/PAAG-SI/OA/2019 study will be used as a control. It is assumed that continued monitoring of patients in the placebo group will not lead to the detection of new adverse events (AE), the frequency of which should be compared with the frequency in the active therapy group, and is connected to unethical restriction of patients in the placebo group in the possibility of using potentially effective synovial fluid endoprostheses.

The open study provides follow-up of patients for 6 months (up to 25 weeks from Visit 1).

Thus, the maximum duration of participation in the study for one patient will be a maximum of 172 days.

Patient visits

Visit 0 (Day 0, -24 h -0 h, screening)

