- Assessment of the severity of pain in the target knee joint using 100-mm VAS;
- Evaluation of the effectiveness of treatment by the patient, OEP parameter;
- Evaluation of the effectiveness of treatment by the investigator, OEI parameter;
- Clinical blood test (hemoglobin level, hematocrit, red blood cell count, white blood cell formula, platelet count, ESR);
- Biochemical blood test (glucose, ALT, AST, ALP, GGTP, total bilirubin, creatinine, uric acid, rheumatoid factor);
- Coagulogram (APTT, PT, prothrombin index, fibrinogen)
- General urinalysis (color, transparency, relative density, pH, glucose, protein, ketone bodies, urobilinogen);
- Injection of the studied MD into the cavity of the target joint (only for patients of Group B who are shown to receive the injection according to the criteria specified in the Protocol, and didn't receive the injection at Visit 1);
- Evaluation of the patient's diary;
- Evaluation of the total number of paracetamol tablets taken (one tablet = 500 mg) using patient's diary, PARACETAMOL parameter;
- Evaluation of the patient's diary of the total number of NSAIDs allowed by the Protocol in case of paracetamol inefficiency (NSAIDs allowed by the Protocol in case of paracetamol inefficiency: diclofenac potassium tablets 50 mg, diclofenac sodium tablets 75 mg, naproxen tablets 500 mg, naproxen sodium tablets 550 mg, meloxicam tablets 7.5 mg, celecoxib tablets 200 mg), NSAID parameter;
- Issuing a new patient diary to the patient;
- Registration of AE and SAE;
- Evaluation of exclusion criteria.

Every 2 weeks, between Visit 3 and Visit 4 (weeks 15, 17, 19, 21 and 23), telephone contacts are made with the patient to clarify complaints, AE and the need for taking paracetamol or NSAIDs for the past 2 weeks. If AE is detected, or the need to take paracetamol or NSAIDs more than 4 days a

week in each of the consecutive 2 weeks, the patient is invited to the clinic for an unscheduled Visit or a Visit to prematurely complete participation in the study (depending on the reason for the visit).

Visit 4 (Week 14, Day 91 ± 2, treatment and follow-up) - as indicated

Only patients who received an injection of MD NOLTREXTM into the target knee joint on Visit 3 are eligible for Visit 4.

The following procedures must be performed during the visit:

- Measurement of the body weight;
- Collection of complaints and anamnesis;
- Registration of concomitant therapy;
- Assessment of the main vital signs (BP, HR, RR, body temperature);

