- Physical examination of joints;
- Assessment of the severity of pain in the target knee joint using 100-mm VAS;
- Injection of the studied MD into the target joint cavity (only for patients of Group B, in which the severity of pain in the target knee joint using 100 mm VAS did not decrease by 40% or more compared to the assessment at Visit 3)
- Evaluation of the patient's diary;
- Return of the diary to the patient;
- Registration of AE and SAE;
- Evaluation of exclusion criteria.

Visit 5 (Week 25, Day 169 ± 2 , follow-up)

- Measurement of the body weight;
- Collection of complaints and anamnesis;
- Registration of concomitant therapy;
- Assessment of the main vital signs (BP, HR, RR, body temperature);
- Physical examination of joints;
- Radiography of the knee joints and documentation of parameters of joint space width (JSW) and joint space narrowing (JSN);
- Filling out algofunctional questionnaire WOMAC with an assessment of the subscales of pain (WOMAC-A), stiffness (WOMAC-B) and functional performance (WOMAC-C);

- Assessment of the severity of pain in the target knee joint using 100-mm VAS;
- Evaluation of the effectiveness of treatment by the patient, OEP parameter;
- Evaluation of the effectiveness of treatment by the investigator, OEI parameter;
- Clinical blood test (hemoglobin level, hematocrit, red blood cell count, white blood cell formula, platelet count, ESR);
- Biochemical blood test (glucose, ALT, AST, ALP, GGTP, total bilirubin, creatinine, uric acid, rheumatoid factor);
- Coagulogram (APTT, PT, prothrombin index, fibrinogen);
- General urinalysis (color, transparency, relative density, pH, glucose, protein, ketone bodies, urobilinogen);
- Evaluation of the patient's diary;
- Evaluation of the total number of paracetamol tablets taken (one tablet = 500 mg) using patient's diary, PARACETAMOL parameter;
- As per patient's diary, evaluation of the total number of NSAIDs allowed by the Protocol in case of paracetamol inefficiency (NSAIDs allowed by the Protocol in case of paracetamol inefficiency: diclofenac potassium tablets 50 mg, diclofenac sodium tablets 75 mg, naproxen tablets 500 mg, naproxen sodium tablets 550 mg, meloxicam tablets 7.5 mg, celecoxib tablets 200 mg), NSAID parameter;
- Registration of AE and SAE;
- Evaluation of exclusion criteria.

An unscheduled visit

The following procedures must be performed during the visit:

- Measurement of the body weight
- Collection of complaints and anamnesis;

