## 3.4. Applicable level of significance

Statistical analysis of all the presented efficacy and safety parameters will be carried out at a 5% significance level, using two-way versions of statistical criteria.

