## **3.6.** Procedures to count the missing, non-analyzable, and questionable data

During the monitoring visits to the clinical center, the monitoring specialists authorized by the sponsor will conduct an analysis of patient's eCRF to identify any lack of necessary data. In the absence of data in the eCRF and the availability of relevant information in the primary documentation, the questions to the investigators and instructions for eliminating the inconsistencies will be formulated.

The statistician, authorized by the sponsor, and the principal investigator, when checking the database of research results, will analyze for the presence of dubious, missing and non-analyzable data, and will also formulate questions for investigators.

Researchers, if possible, will eliminate the identified errors in eCRF and inform the main researcher and authorized representatives of the sponsor about this. If the detected errors in the data cannot be eliminated after the completion of patient participation in the study, the statistical analysis of the data will be used to analyze the sensitivity of the resulting parameters to the doubtful data found. Information about the missing, doubtful and non-analyzable data will be presented in the final clinical trial report.

For all parameters of efficacy, safety and tolerability, data recovery is not provided due to the fact that the distribution of patients into subgroups for analysis is based on the actual need for treatment, and is not based on any procedures for distribution into groups, so the missing values cannot be considered as missing accidentally or completely accidentally.

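### The Visit 3 subgroup tests compare groups sorted mainly by the Visit 3 pain score, and the late course has no planned change from its own starting value

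*SAP*

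**What the plan says.** **How the subgroups arise.** Under the protocol's study design, Group B is not injected at Visits 1 and 2. It holds patients whose VAS at inclusion is at least 40% below Visit 1 of the 2019 study, "or those who cannot be re-injected with MD NOLTREXTM". At Visit 3 each Group B patient is reassessed. The condition begins "If at Visit 3 of the open study pain remains the same in the target joint of the study IA/PAAG-SI/OA/2019 or increases in intensity" and extends to any fall of less than 40% from the 2019 Visit 1 score. Patients who meet it and have no contraindication are injected and become the subgroup re-treated at Visit 3. The rest of Group B is the one-course-only subgroup. The third subgroup is re-treated at Visit 1.

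**What is tested.** SAP 3.1.3, parameter 4, takes VAS change on the "100-mm VAS at Visit 2 (week 1), Visit 3 (week 13), Visit 5 (week 25) compared to the basal value at Visit 0" of the open study and from Visit 1 of the 2019 study. The WOMAC changes use the same two baselines at Visits 3 and 5. On testing, SAP 3.1.3 says "For comparison between these subgroups, variance analysis will be used (for quantitative parameters other than those based on WOMAC". WOMAC gets ANCOVA with the starting WOMAC of the double-blind study as covariate, and pairwise comparisons follow if needed. SAP 3.4 adds: "Statistical analysis of all the presented efficacy and safety parameters will be carried out at a 5% significance level".

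**What the SAP acknowledges.** SAP 3.6 states that "the distribution of patients into subgroups for analysis is based on the actual need for treatment", but uses this only to rule out imputation.

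**The late course.** In the protocol's visit schedule, "Only patients who received an injection of MD NOLTREXTM into the target knee joint on Visit 3 are eligible for Visit 4". The second late injection goes to patients whose VAS "did not decrease by 40% or more compared to the assessment at Visit 3".

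**The concern.** The Visit 3 VAS does two jobs. It decides which Group B patients are re-treated, and it is then an outcome on which the resulting subgroups are tested. Neither subgroup has had an open-study injection when that score is taken, so a significant difference says nothing about treatment. A reader of the report could take it as an efficacy finding.

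Separately, the subgroup re-treated at Visit 3 is never summarised from its pre-injection value. Its late-course change is spread over two planned rows and carries no SD or confidence interval of its own, although SAP 3.1 promises a 95% CI for means. The early course has a one-week VAS endpoint (Visit 2). The late course's counterpart (Visit 4) is measured but is not among the efficacy parameters.

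**Working it through.** The plan states no power or sample-size figure to reproduce, only a cap of 72 patients and a two-sided 5% level.

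**1. The split, by reading.** Take patients with a 2019 Visit 1 VAS of 70 mm. The 40% rule puts the cut at 0.6 × 70 = 42 mm. Among Group B patients without a contraindication, everyone at or below 42 mm at Visit 3 stays in the one-course subgroup and everyone above 42 mm is re-treated. As percentage change from 2019 Visit 1, the two sets do not overlap. Only contraindicated patients, who stay in the one-course subgroup whatever their pain, blur the split.

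**2. Size of the false signal, by simulation with no treatment effect.** From the documents: N = 72, the 40% rule at Visits 0 and 3, and a two-sided 5% test. Assumed, because the documents give no values:
- 2019 VAS normal with mean 65 and SD 12, clipped to 40–100
- later VAS with mean 40 + 0.4 × (baseline − 65), SD 20 and a shared person effect, clipped to 0–100
- between-visit correlation r of 0.5 to 0.9
- 0% or 20% contraindicated at Visit 0, with none or half of these cleared by Visit 3

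Each setting had 2,000 trials (1,500 for WOMAC at VAS–WOMAC correlations 0.5 and 0.8). Trials with fewer than 3 patients in a subgroup were dropped (0–20%).

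One-course-only versus re-treated at Visit 3, VAS change at Visit 3, share of trials significant at r = 0.5 / 0.7 / 0.9:

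| Contraindicated | From Visit 0 | From Visit 0, Tukey |
|---|---|---|
| None | 0.996 / 0.981 / 0.869 | 0.969 / 0.919 / 0.693 |
| 20%, none cleared | 0.975 / 0.947 / 0.813 | 0.929 / 0.851 / 0.625 |
| 20%, half cleared | 0.935 / 0.839 / 0.521 | 0.857 / 0.726 / 0.361 |

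- With no contraindicated patients, the gap produced by sorting alone was 23.9 / 19.1 / 11.0 mm.
- Against 2019 Visit 1 the rates were 0.997–1.000 (none contraindicated), 0.909 / 0.775 / 0.388 (none cleared) and 0.996 / 0.992 / 0.961 (half cleared).
- The three-subgroup ANOVA of change from Visit 0 rejected in 54–99.9%.
- WOMAC-T ANCOVA with the 2019 covariate, for a same-visit VAS–WOMAC correlation of 0.5–0.8 and no contraindicated patients, rejected in 26–83%. A covariate from the 2019 study cannot remove selection on a later score.

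A second set of assumptions (mean reduction 35–55%, residual SD 22 mm, r = 0.3–0.8, 0–30% ineligible; 3,000 trials per setting) gave 88–100% from Visit 0 and 66–100% from 2019 Visit 1. As a control, a random split into 30 and 8 patients rejected in 4.6%.

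**3. The missing late-course change.** Take VAS 70 (2019 Visit 1), 35 (Visit 0), 55 (Visit 3) and 35 (Visit 5). At Visit 0 the fall is 35/70 = 50%, so the patient enters Group B. At Visit 3 it is 15/70 = 21%, so the patient is re-treated.

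| Baseline | Visit 3 | Visit 5 |
|---|---|---|
| Visit 0 | +20 | 0 |
| 2019 Visit 1 | −15 | −35 |

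The late-course change, 35 − 55 = −20, is in neither row. A subgroup mean can be recovered by subtraction if data are complete, but its SD cannot. If both planned changes have SD s and correlation c, the SD of their difference is s√(2(1 − c)). That is 1.41s at c = 0 and 0.45s at c = 0.9, and c is not among the planned statistics.

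**4. What the added row would show with no effect.** Visit 5 minus Visit 3 in the re-treated subgroup averaged −3.6 to −11.5 mm under the first assumptions and about −9 to −16 mm under the second. This is regression to the mean. Under the first assumptions the mean subgroup size was 4–13 and the 95% CI half-width 8–14 mm.

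**The case against.** Safety is the main purpose (SAP 3.8). No success criterion rests on a subgroup p-value, all-patient efficacy is descriptive, pairwise tests are only conditional, and SAP 3.1 calls itself a brief account. This limits the severity. It does not exempt Visit 3, because SAP 3.1.3 and 3.4 still prescribe the tests and the overall three-subgroup test is affected too.

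The percentages depend on assumed inputs, and the contraindication list is broad. With 40% contraindicated and none cleared, the pairwise test against 2019 Visit 1 rejects in only 57% / 33% / 6% at r = 0.5 / 0.7 / 0.9 (42% of trials dropped at 0.9). For that one contrast the distortion can therefore nearly vanish. In the same setting, change from Visit 0 (75–93%) and the three-subgroup ANOVA (69–98%) remain far above 5%.

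The 2019 baseline does show the worked patient improving, and net change from a fixed baseline is a legitimate summary. Patient-level data would also yield the missing SD directly. The gap is thus one of planned reporting, not of data.

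The proposed Visit 5 minus Visit 3 row starts from a value selected for being high. With no effect, its 95% CI excluded zero in 18–54% of trials. This stands, and the row needs its warning. Removing the Visit 3 test also leaves a Visit 5 test of the same two subgroups, which rejected in about 11–24% of null trials for change from Visit 0. This widens the problem and does not answer it.

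**Conclusion.** The concern holds and should be fixed. The direction follows from the documents alone: the rule that forms the two Group B subgroups uses the variable then tested. The size rests on assumed VAS means, SDs, correlations and contraindication rates. Under the main settings, a nominal 5% pairwise test of VAS change from Visit 0 rejects in 52–99.6% of trials with no treatment effect, or 36–97% after Tukey. The lowest figures come from high between-visit correlation with half of the contraindicated patients cleared. WOMAC is affected less, and only through its correlation with VAS. The absence of any change from Visit 3, and of Visit 4 VAS as an endpoint, is a matter of reading and needs no assumption. The safety objective is untouched.

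**What to change.** 1. Remove the inferential Visit 3 comparison between subgroups in SAP 3.1.3. Show Visit 3 values descriptively, and state that the Group B subgroups are formed mainly on Visit 3 VAS. Do not substitute a test of Group A against Group B: that split is made on Visit 0 VAS and rejected in 23–96% of the same null trials for change from Visit 0.
2. For the subgroup re-treated at Visit 3, add descriptive rows with 95% CIs: Visit 5 minus Visit 3 (WOMAC and VAS), Visit 4 minus Visit 3 (VAS), and paracetamol and NSAID totals from Visit 3 to Visit 5.
3. State beside the Visit 5 minus Visit 3 rows that they include regression to the mean, that their CIs may exclude zero without any effect, and that they do not estimate a treatment effect.
4. Label as exploratory any adjusted comparison of re-treated with not re-treated Group B patients. Among patients without a contraindication the 40% rule leaves no overlap. If 20% are contraindicated, only about 4–7 of them would have a high Visit 3 VAS. Put the same caution on the Visit 5 subgroup tests.

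The cost is SAP wording and a few table rows. All values are already collected, and no visit, procedure or treatment rule changes.

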Procedures at Visit 5 of study IA/PAAG-SI/OA/2019 (hereinafter referred to in the Protocol as Clinical study 1 - CS1) that coincide with the screening Visit procedures (Visit 0) in study IA/PAAG-SI/OA/2020 will be counted as the procedures of Visit 0 of study IA/PAAG-SI/OA/2020, there is no need to repeat the identical procedures of these visits.

- The signing of the informed consent;
- The collection of demographic data;
- Measurement of the body weight;
- Collection of complaints and anamnesis;
- Registration of concomitant therapy;
- Assessment of the main vital signs (blood pressure [BP], heart rate [HR], number of respiratory movements [RR], body temperature);
- Physical examination of joints;

- Completing an algofunctional questionnaire for evaluating the osteoarthritis index developed by researchers at the Western Ontario and McMaster Universities Osteoarthritis, WOMAC with an assessment of subscale pain (WOMAC-A), stiffness (WOMAC-B), and functional performance (WOMAC-C) (from *Visit 5 of CS1*);
- Assessment of the severity of pain in the target knee joint by 100-mm VAS (from *Visit 5 of CS1*);
- Evaluation of the effectiveness of treatment by the patient, parameter OEP (from *Visit 5 of CS1*);
- Evaluation of the effectiveness of treatment by the investigator, parameter OEI (from *Visit* 5 of CS1);
- Documenting the target knee joint (the same joint that was identified as the target in the IA/PAAG-SI/OA/2019 study);
- Clinical blood test (hemoglobin level, hematocrit, red blood cell count, white blood cell count, white blood cell formula, platelet count, ESR) (from *Visit 5 of CS1*);
- Biochemical analysis of blood (glucose, alanine aminotransferase [SPGT], aspartate aminotransferase [AST], alkaline phosphatase [ALP], gamma-glutamyltranspeptidase [GGTP], total bilirubin, creatinine, uric acid, rheumatoid factor) (from *Visit 5 of CS1*);
- Coagulogram (APTT, PT, prothrombin index, fibrinogen) (from *Visit 5 of CS1*);
- Blood tests for antibodies to human immunodeficiency virus (HIV), hepatitis b surface antigen (HBsAg) and antibodies to Hepatitis C Virus (anti-HCV]), syphilis (RW);
- General urinalysis (color, transparency, relative density, pH, glucose, protein, ketone bodies, urobilinogen) (from *Visit 5 of CS1*);
- Rapid urine test for pregnancy in women with preserved reproductive potential (from *Visit* 5 of CS1);
- Evaluation of inclusion/non-inclusion criteria;
- Issuing a patient's diary;
- Check AE and serious AE (SAE).

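### OEP and OEI have no stated reference treatment or time point, yet SAP 3.1.3 tests them between subgroups with different treatment histories and without adjusting for the Visit 0 rating

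*SAP*

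**What the plan says.** SAP 3.1.3, item 5, lists "Evaluation of the effectiveness of treatment by the patient, parameter OEP (on a scale from 1-clear deterioration to 6-significant improvement". Item 6 is the investigator's counterpart: "Evaluation of the effectiveness of treatment by the investigator, parameter OEI (on a scale from 1-clear deterioration to 6-significant improvement". Both are taken at Visits 3 and 5, which gives four parameters.

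The Protocol's visit schedule collects the patient rating at Visit 3 ("Evaluation of the effectiveness of treatment by the patient, OEP parameter") and the investigator rating with it, from all patients. On treatment before that visit, the Protocol's study design says of Group A: "The course in an open study is a maximum of 2 injections (the first - at Visit 1, the second - at Visit 2". Of patients with a sufficient pain response, or who cannot be re-injected, it says that "a re-injection of MD NOLTREXTM will not be performed on Visits 1 and 2 of the open study (Group B". Group B's first possible open-study injection is at Visit 3, and the schedule lists it after the ratings: "only for patients of Group B who are shown to receive the injection according to the criteria specified in the Protocol".

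A starting value exists. The Visit 0 procedures include "Evaluation of the effectiveness of treatment by the patient, parameter OEP", carried over from Visit 5 of the 2019 study, and the same holds for OEI.

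SAP 3.1.3 sends all efficacy parameters into three subgroups defined by the courses actually received: the 2019 course only, re-treated from Visit 1, and re-treated from Visit 3. It then says: "For comparison between these subgroups, variance analysis will be used" for quantitative parameters other than WOMAC, covariance analysis for WOMAC, and chi-square for qualitative parameters. SAP 3.4 sets a two-sided 5% level.

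**The concern.** A scale that runs from deterioration to improvement measures change from something. If that something is not stated, a patient injected at Visit 1 may rate the re-injection. A patient with only the 2019 course must rate that course, or the change since Visit 0.

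The choice matters here because the subgroups are formed largely on pain response: at Visit 0 for Group A versus Group B, and at Visit 3 for the split within Group B. A patient whose pain has fallen by 40% or more since 2019 is much improved against 2019 and about unchanged against Visit 0. A between-subgroup difference could then reflect the reference in the rater's mind, or the way the groups were formed, and be read as an effect of one versus two courses.

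**Working it through.** **1. Starting points in SAP 3.1.3, side by side**

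| Item | Parameter | Stated starting point |
|---|---|---|
| 1–3 | WOMAC total and subscales | Visit 0 of the open study, and Visit 1 of the 2019 study |
| 4 | VAS pain | the same two |
| 5, 6 | OEP, OEI | none |
| 7, 8 | Paracetamol and NSAID tablets | Day 1 |
| 9 | JSN | Visit 0 of the 2019 study |

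Only OEP and OEI lack one. Only WOMAC receives a baseline covariate.

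**2. Time from the start of the latest course to the rating**

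Inputs are the Protocol's nominal days: Visit 1 = Day 1, Visit 3 = Day 84, Visit 5 = Day 169. The 2019 course is placed 25 weeks before Visit 1, because Visit 0 coincides with the 2019 week-25 visit.

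| Subgroup | At Visit 3 | At Visit 5 |
|---|---|---|
| Re-treated from Visit 1 (Group A) | (84 − 1)/7 = 11.9 weeks | (169 − 1)/7 = 24.0 weeks |
| Re-treated from Visit 3 (Group B) | 25 + 11.9 = 36.9 weeks | (169 − 84)/7 = 12.1 weeks |
| 2019 course only (Group B) | 36.9 weeks | 25 + 24.0 = 49.0 weeks |

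**3. What the reference could do to the contrast**

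The plan has no figure to reproduce: it gives no VAS data, no A/B split and no sample size calculation. All inputs here are therefore assumptions.

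- 2019 baseline VAS: mean 65, SD 10.
- Visit 0 VAS: mean 30 to 38.
- SD of the change from Visit 0 to Visit 3: 8 to 12. No treatment effect.
- Group A if Visit 0 VAS exceeds 60% of the 2019 baseline, otherwise Group B.
- Rating 1 to 6 from mm improvement against the reference, cut at −20, −7, 7, 20 and 35.

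| Reference used at Visit 3 | B minus A in mean OEP |
|---|---|
| Both groups rate against 2019 | +1.0 to +1.7 |
| B against 2019, A against Visit 0 | +2.0 to +2.5 |
| Both groups rate against Visit 0 | −0.2 to −0.6 |
| Both against 2019, adjusted for the Visit 0 rating | 0.0 to +0.2 |

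I reran this over 24 scenarios with 400,000 patients each. Visit 0 SD was 12, 16 or 18, and the correlation of stable pain with the 2019 baseline was 0 or 0.5. Visit noise was independent, and VAS was held within 0 to 100. The four rows became +0.5 to +1.7, +1.8 to +2.5, −0.2 to −0.8, and 0.0 to +0.3. With mixed references, adjusting for the Visit 0 rating still left +1.5 to +2.3. The covariate therefore helps only when the reference is common.

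**4. Whether a test would pick up such a shift**

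Assume subgroup sizes of 24/24/24 or 36/24/12 and a pure shift of reference in one subgroup. At 0.5 SD, chi-square rejects in about 15–16% of trials and ANOVA in about 36%. At 1.0 SD the figures are 65–66% and 92%. With no shift they are about 4% and 5–6%. SAP 3.1 classes ordinal data as qualitative, so chi-square would apply if the ratings are treated as ordinal. SAP 3.1.3 does not say which test is meant.

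**The case against.** Group B does have a treatment to rate. Everyone received the device in the 2019 study, the stated purpose covers a single or a repeated course, and patients with one course are a named subgroup. At Visit 0 only the 2019 course could be rated. If raters keep that frame, the starting point is common and one versus two courses is the intended contrast. The rating forms are not among the documents and may already print a reference. All of this stands. A reader might infer that the subgroups are in fact answering about different treatments, but the documents do not show it. They support only that the SAP states no reference and that the answers may differ.

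A reader might also infer that mixed references reverse the sign of the contrast. They do not: mixed references and a common 2019 reference both give a positive difference. The negative sign appears only when both groups rate against Visit 0, and in a no-effect model that is regression to the mean after grouping on Visit 0 pain.

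A further objection is that stating a 2019 reference leaves a spurious difference of a point or more, so it cures nothing. That holds for a stated reference alone. It is largely met once the Visit 0 rating is added as covariate.

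The simulation inputs are invented. The model also omits patients placed in Group B because one of the ten criteria against re-injection applies, whatever their pain. The documents do not say how many these are. SAP 3.1.1 may well compare the Visit 0 ratings as initial characteristics, but that does not adjust the tests in 3.1.3.

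**Conclusion.** The concern holds in this form: the SAP leaves the reference for OEP and OEI unstated, the subgroups have different treatment histories when they rate, and the ratings are tested without the available Visit 0 value. It affects four parameters, OEP and OEI at weeks 13 and 25.

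The illustrated size, from −0.2 to −0.6 up to +2.0 to +2.5 points on a six-point scale with no treatment effect, rests wholly on assumed VAS values and cut points. It shows that the contrast is sensitive to the reference, and it does not predict a result.

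Priority is modest. Safety is the main purpose, the all-patient efficacy analysis is descriptive, and WOMAC and VAS carry explicit baselines.

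**What to change.** - Use one stated reference for OEP and OEI, for all patients at Visits 3 and 5. An example is the condition before the first injection in IA/PAAG-SI/OA/2019. Put it on the forms and in SAP 3.1.3, items 5 and 6.
- In SAP 3.1.3, compare the subgroups on OEP and OEI with the Visit 0 rating (from Visit 5 of the 2019 study) as covariate, for example in an ordinal model or ANCOVA.
- If the forms did not use a common reference, report OEP and OEI descriptively within subgroups and drop the between-subgroup test.

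The cost is one sentence on an existing form and one or two in the SAP, with no new data. A 2019 reference means longer recall. Some confounding remains because the subgroups are not randomised. In particular, the split within Group B depends on pain at Visit 3, the same visit as the week-13 rating. The Visit 0 covariate does not remove that overlap, so the contrast between those two subgroups at week 13 should be read with particular caution.
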